Biostatistician
Division of Biostatistics
Clinical Research Office, Loyola University Chicago
[name]
[name]
Email: [contact]

Research Office: Clinical Research Office (CRO)
Stritch School of Medicine, Loyola University Chicago
[name]
[name]
[name]
[contact]
[contact]

LU 210546

Version 10/23/17

Signature Page

The signature below constitutes the approval of this protocol and the attachments, and provides the necessary assurances that this trial will be conducted according to all stipulations of the protocol, including all statements regarding confidentiality, and according to local legal and regulatory requirements and applicable U.S. federal regulations and ICH guidelines.

Principal Investigator (PI) Name: _____

PI Signature: _____

Date: _____

[figure not shown]
STUDY SUMMARY	
Title	BEACON - A phase I/II study of high-dose-rate Brachytherapy and External beam and short-term Androgen deprivation CO mbined for the treatment of Men with Fluciclovine PET Pelvic Nodal Uptake in locally recurrent prostate cancer after prior definitive radiotherapy
Short Title	Combined salvage high dose rate brachytherapy, external beam and short-term hormonal therapy for local recurrent prostate cancer with fluciclovine PET uptake in pelvic nodes after radiotherapy
Protocol Number	***
Methodology	Phase I/II Non-randomized trial
Study Duration	5 years
Study Center(s)	Loyola University medical Center, Stritch School of Medicine, Loyola University Chicago
Objectives	
 1. To determine the 3 month grade ≥ 3 radiation-related genitourinary and gastrointestinal toxicity of this treatment approach (primary endpoint) 2. To describe the acute and late toxicity profile with this approach 3. To evaluate disease control efficacy outcomes (biochemical progression-free survival, local control, regional recurrence, cause-specific survival, overall survival, etc.) 4. To evaluate patient reported health related quality of life following this treatment approach 5. To describe the dosimetry in patients undergoing this approach
Number of Subjects	24

LU 210546

Version 10/23/17

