2.0 STUDY OBJECTIVES

2.1 *Primary Objective*

2.1.1 To determine the incidence of acute grade ≥ 3 radiation-related genitourinary (GU) and gastrointestinal (GI) toxicity of this treatment approach

2.2 *Secondary Objectives*

- 2.2.1 To describe the acute and late toxicity profile with this approach
- 2.2.2 To evaluate disease control efficacy outcomes (biochemical progression-free survival, local control, regional recurrence, cause-specific survival, overall survival, *etc.*)
- 2.2.3 To evaluate patient reported health related quality of life following this treatment approach
- 2.2.4 To describe the dosimetry in patients undergoing this approach

2.3 *Endpoints*

2.3.1 Primary Endpoint:

2.3.1.1 3-month radiation-related grade ≥ 3 GU and GI toxicity as defined by Common Terminology Criteria for Adverse Events (CTCAE) v4.03 (Link available in Appendix A).

2.3.2 Secondary Endpoints:

2.3.2.1 All-grade acute and late toxicity as defined by CTCAE v4.03 criteria (see Appendix A)

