8.1.11 Labs

AST, ALT, Alkaline Phosphatase, and any labs required for the brachytherapy procedure as part of usual care.

8.2 *Follow-up Procedures*

Patients will be followed as described in Section 8.3.

8.3 *Study Parameters*

	Pre-study	Start of EBRT	Week 4 post-treatment	Month 3 & 6	Month 12	Follow-up Q 6 months*	Time of Biochemical Recurrence
Informed Consent	X						
History and PE, including DRE	X		X	X	X	X	
Medication Assessment	X		X	X	X	X	
Performance Status	X		X	X	X	X	
Toxicity Assessment			X	X	X	X	
PSA	X			X	X	X	
Bone scan	X						X
MP-MRI	X						X¥
PET/CT	X						
IPSS score	X		X	X	X	X	
EPIC-26	X		X	X	X	X	
AST/ALT/ALK PHOS	X	X					

* Until disease progression, death, or follow up period is complete

¥If MP-MRI reveals any suspicious lesions, then biopsy is encouraged.

DRE – Digital Rectal Exam

PE – Physical Exam

MP – Multi-parametric

EBRT – External Beam Radiotherapy

8.4 *Removal of Subjects from Study*

Patients can be taken off the study treatment and/or study at any time at their own request, or they may be withdrawn at the discretion of the investigator for safety, behavioral, or administrative reasons. The reason(s) for discontinuation will be documented and may include:

- 8.4.1 Patient voluntarily withdraws prior to treatment;
- 8.4.2 Patient withdraws consent (termination of treatment and follow-up);
- 8.4.3 Patient is unable to comply with protocol requirements;
- 8.4.4 Patient develops interval co-morbidity that makes continuation in the protocol unsafe;
- 8.4.5 Treating physician(s) judge(s) the study would not be in the patient's best interest;
- 8.4.6 Development of second malignancy (except for basal cell carcinoma or squamous cell carcinoma of the skin) that requires treatment, which would interfere with this study;
- 8.4.7 If a research subject cannot be located to document survival after a period of 2 years; the subject may be considered "lost to follow-up". All attempts to contact the subject during the two years must be documented and approved by the Data Monitoring Committee.

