9.0 MEASUREMENT OF EFFECT

9.1 *Antitumor Effect- Solid Tumors*

9.1.1 Definitions:

Evaluable for toxicity: All patients will be evaluable for toxicity immediately following brachytherapy.

Evaluable for disease control assessment: All patients with at least 2 follow-up PSAs will be evaluable for disease control. After brachytherapy, these patients will have their disease status classified according to the definitions stated below.

Biochemical (PSA) recurrence (BR): Based on RTOG Phoenix definition: an increase of the PSA level at least 2 ng/ml greater than the minimum level after therapy (REF: phoenix paper)

All patients with BR should undergo at least MP-MRI of the prostate and bone scan. Biopsy of any suspicious lesions within the prostate gland on MP-MRI is encouraged.

Freedom from Biochemical (PSA) Recurrence (FFBR):

The time to PSA failure will be measured from the date of treatment to the date of a rise by 2 ng/mL or more above the nadir PSA. The time of failure will be the date of the first PSA that is 2 ng/mL or more above the lowest prior post-treatment PSA value. If the rise in PSA to $>$ nadir + 2 occurs during the first 36 months followed by a subsequent non-hormonal induced PSA decrease, patients will **not** be considered PSA failures.

As a benign “spike” or “bounce” in the PSA value has been described in as many as 35% of patients 12-36 months following brachytherapy, intervention for a PSA failure should be based on a positive prostate biopsy at least 24 months post-treatment and/or clinical evidence of distant relapse (i.e., bone scan, CT scan, etc).

Local Failure (LF): This rating will be assigned when there is biopsy-proven disease progression or recurrence at the lesion within the prostate treated with protocol therapy. Histologic criterion for local failure is the presence of prostatic carcinoma upon biopsy more than 2 years after the start of treatment. Residual carcinoma on biopsy should show minimal radiation effect and should be in clinical scenario of increasing PSA.

Local Control (LC): Absence of local failure. This will be assumed in patients with a controlled PSA and for those with PSA failure but no radiographic, clinical, or biopsy-proven disease at the lesion treated with protocol therapy.

Freedom from Local Failure (FFLF): The time to local progression will be measured from the date of treatment to the date of local failure.

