Elsewhere Prostate Failure (EPF): This rating will be assigned when there is biopsy-proven disease progression/recurrence at outside the lesion treated with protocol therapy but within the prostate or seminal vesicles.

Elsewhere Prostate Control (EPC): Absence of EPF. Will be assumed in patients with a controlled PSA and in patients with PSA failure but no radiographic, clinical, or biopsy-proven disease at the site treated with protocol therapy.

Freedom from Elsewhere Prostate Failure (FFEPF): The time to elsewhere prostate failure will be measured from the date of treatment to the date of EPF.

Regional Failure (RF): Visible disease on imaging that occurs in lymph nodes within the usual regional spread pattern of prostate cancer

Regional Control (RC): Absence of regional/nodal recurrence.

Freedom from Regional Failure (FFRF): The time to regional failure will be measured from the date of treatment to the date of RF.

Distant Metastasis (DM): Visible disease on imaging that occurs elsewhere in the body including non-regional lymph nodes.

Freedom from Distant Metastasis (FFDM): The time to distant metastasis will be measured as the date of treatment to the date of DM.

Freedom from hormone therapy (FFHT): The time from the date of treatment to first administration of androgen deprivation therapy

Disease-free Survival (DFS): Defined as the duration of time from the date of completion of treatment to either BR, LF, EPF, RF, DM, or death.

Cause-specific Survival (CSS): Defined as the duration of time from the date of completion of treatment to death from prostate cancer.

Overall Survival (OS): Defined as the duration of time from the date of completion of treatment until death from any cause.

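### After Month 12, scheduled visits stop at an undefined disease progression, so later metastasis, hormone-therapy start, cause of death and new late toxicity have no collection schedule

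*Combined protocol and SAP*

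**What the plan says.** Section 8.2 gives no follow-up duration of its own: "Patients will be followed as described in Section 8.3". The Section 8.3 table has visits at Week 4, Months 3 and 6, and Month 12, then a column of six-monthly visits. Only that last column carries the footnote "Until disease progression, death, or follow up period is complete". It holds the history and examination, medication review, performance status, toxicity assessment, PSA, IPSS and EPIC-26. The follow-up period has no stated length; the Study Summary says only "Study Duration 5 years", not split between accrual and follow-up.

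At biochemical recurrence, Section 9.1.1 requires one work-up: "All patients with BR should undergo at least MP-MRI of the prostate and bone scan". The table schedules nothing after it.

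Several listed endpoints extend beyond that point. Section 2.3.2.1 lists "All-grade acute and late toxicity as defined by CTCAE v4.03 criteria" with no late time window. Section 9.1.1 defines freedom from distant metastasis by imaging, freedom from hormone therapy by the first administration, and cause-specific survival as follows: "Defined as the duration of time from the date of completion of treatment to death from prostate cancer".

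Other sections keep some observation going. Section 13.6.1 has adverse events and survival status entered in the database. Section 8.4.7 covers a man who "cannot be located to document survival after a period of 2 years". Section 10.2 follows adverse events already identified.

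**The concern.** Men whose disease recurs are the ones at risk of metastasis, renewed hormone therapy and prostate-cancer death, and they are the men whose scheduled visits end. If what happens to them afterwards is found only by chance, freedom from distant metastasis and cause-specific survival are estimated mainly from men still in remission and tend to look too good. A crude late-toxicity proportion would be too low, because some men are no longer assessed but stay in the denominator.

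The definitions in Section 9.1.1 add to this. Local control and elsewhere-prostate control are assumed in men with PSA failure but no documented disease, so a man who is not examined counts as controlled.

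This matters because Section 1.5 intends the data to support a phase III comparison of disease control and survival.

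**Working it through.** **1. The plan's own figures.** The only design figures belong to the toxicity test in Section 12.2. With stopping at 2 or more toxic responses in 7, and rejection at 4 or fewer in 24, the exact binomial calculation gives:
- at a toxicity rate of 0.33: early stopping 0.730 and type I error 0.0462 (plan: 73% and .046);
- at 0.10: power 0.809 (plan: 81%).

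They reproduce. The endpoint in Section 2.3.1.1 is read at 3 months, before any footnoted visit, so this point does not touch them.

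**2. What is scheduled after progression, once past Month 12.**

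| Item | Scheduled source | Other provision |
|---|---|---|
| Metastasis present at biochemical recurrence | Bone scan and MP-MRI | – |
| Later metastasis | None | Section 13.6.1, no timetable |
| First hormone therapy | None (medication review stops) | Section 13.6.1, no timetable |
| New late toxicity | None | Adverse events entered (13.6.1); 10.2 covers known events only |
| Survival status | None | 13.6.1 and 8.4.7 |
| Cause of death | None | Not mentioned |

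Section 13.6 takes its data timeframes from the Section 8.3 table, so the database provision inherits the footnote.

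**3. Conflict with Section 9.1.1 if a PSA rise counts as progression.** Section 9.1.1 defines biochemical, local, elsewhere-prostate, regional and distant failure, but not progression.
- The bounce rule withdraws a PSA failure in the first 36 months if PSA then falls without hormones. That needs a later PSA, which would no longer be scheduled.
- The histologic criterion for local failure needs a biopsy more than 2 years after the start of treatment. Visits could end before then.

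**4. Direction and possible size (illustration on assumed inputs).** The two salvage HDR series cited in Section 1 report five-year biochemical control of 68.9% and 51%. In 24 men that would be 24 × 0.311 = 7.5 and 24 × 0.49 = 11.8 recurrences. Those series treated local recurrence, so they are a rough guide only; 20% is added as a pessimistic case.

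Assume exponential times and let S be the five-year progression-free proportion, with hazard λ = −ln(S)/5. A fraction q of progressors already has metastasis at the recurrence work-up. Of the rest, a fraction d metastasises within 3 years, with hazard μ = −ln(1−d)/3. Then at five years:
- full follow-up: S + (1−q) × [λ/(μ−λ)] × (S − e^(−5μ));
- observation ended at progression, apart from the work-up: S^q.

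For S = 0.69, q = 0.1, d = 0.3: λ = 0.0742, μ = 0.1189 and e^(−5μ) = 0.552. Full follow-up gives 0.69 + 0.9 × 1.66 × 0.138 = 0.90. Ended at progression gives 0.69^0.1 = 0.96.

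| S | q | d | Full follow-up | Ended at progression | Difference (points) | Unrecorded metastases of 24 |
|---|---|---|---|---|---|---|
| 0.69 | 0.1 | 0.3 | 90% | 96% | 6.7 | 1.7 |
| 0.51 | 0.1 | 0.3 | 83% | 93% | 10.3 | 2.9 |
| 0.51 | 0.2 | 0.5 | 73% | 87% | 14.6 | 4.2 |
| 0.20 | 0.1 | 0.3 | 70% | 85% | 14.9 | 5.2 |
| 0.20 | 0.2 | 0.5 | 53% | 72% | 19.9 | 7.5 |

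For cause-specific survival, assume 30% to 50% of progressors die of prostate cancer within 5 years of progression. Full follow-up then gives 95% in the mildest case and 73% in the most severe. It would read 100% only if no death after progression were captured.

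For late toxicity, assume a true five-year rate of 10% or 20%, independent of progression, with visits kept to Month 12. The crude proportion falls to 5.3–8.5% or 10.9–17.0% over the same values of S. A Kaplan-Meier estimate stays unbiased if censoring is independent.

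**The case against.** The strongest reply is that ending clinic visits does not end observation. No section censors any endpoint at progression; Section 9.1.1 defines each one up to its event. Progression is not among the reasons for removal in Section 8.4, and Section 7.0 allows other cancer therapy at progression, which suggests that men remain on study. Section 13.6.1 asks for all follow-up information, the Section 9.0 disease-control parameters, adverse events and survival status. The affected endpoints are secondary and descriptive, in 24 men.

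Much of this stands, and it rules out several stronger readings that a reader might infer:
- *All scheduled follow-up ends at progression.* The footnote is on the six-monthly column only; the first year is unconditional.
- *Cause-specific survival is close to 100% by construction.* That requires no later death to be recorded, which Sections 8.4.7 and 13.6.1 contradict.
- *Overall survival is biased.* Survival status is to be sought and entered, so it is at least partly recoverable.
- *Late toxicity is biased whatever the method.* This is shown for a crude proportion only. A time-to-event estimate loses information but is unbiased if censoring is independent.

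What the reply does not supply is a timetable. Section 13.6 refers back to the table that carries the footnote, Section 8.4.7 schedules no contact, Section 10.2 does not look for new events, and cause of death is mentioned nowhere in these provisions. The absence of a censoring rule in Section 12.3 leaves open whether men will be censored at their last scheduled visit.

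**Conclusion.** The point holds for the period after Month 12. Once disease progresses, later metastasis, first hormone therapy, cause of death and new late toxicity have no scheduled collection, and neither progression nor the length of follow-up is defined. Freedom from distant metastasis and cause-specific survival would tend to read too favourably, since their events mostly follow recurrence; crude late-toxicity rates would tend to read too low.

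The documents cannot give the size. The 7 to 20 points for freedom from metastasis rest on the assumed progression and metastasis rates and on nothing being captured after progression beyond the recurrence work-up. They are a worst case for each set of inputs, not a forecast. The 3-month primary endpoint and the stage-one stopping rule are unaffected.

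If a PSA rise counts as progression, the footnote also conflicts with the bounce rule and the biopsy criterion for local failure, and those passages must be reconciled. The change should be made, but the trial's main test does not depend on it.

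**What to change.** 1. **Section 8.3 footnote.** State that toxicity, metastasis, start of hormone therapy, survival status and cause of death are recorded every 6 months after progression, until death or a common study end date. Chart review or telephone contact is enough; no tests are added.
2. **Definition.** Define disease progression for this footnote consistently with Section 9.1.1. Do not state that PSA visits may end at progression, because the bounce rule needs a later PSA.
3. **Follow-up length.** Split the five years into accrual and follow-up so that the data support the 24-month relapse-free estimate in Section 12.3. Not every man has to reach 24 months, since the method allows censoring, but enough must be at risk then.
4. **Section 12.3.** State that freedom from distant metastasis, cause-specific survival and overall survival are censored at last contact, not at progression.

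The cost is a small amount of extra data collection for a few men at one site. Sample size and the primary analysis do not change.

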9.0 MEASUREMENT OF EFFECT

9.1 *Antitumor Effect- Solid Tumors*

9.1.1 Definitions:

Evaluable for toxicity: All patients will be evaluable for toxicity immediately following brachytherapy.

Evaluable for disease control assessment: All patients with at least 2 follow-up PSAs will be evaluable for disease control. After brachytherapy, these patients will have their disease status classified according to the definitions stated below.

Biochemical (PSA) recurrence (BR): Based on RTOG Phoenix definition: an increase of the PSA level at least 2 ng/ml greater than the minimum level after therapy (REF: phoenix paper)

All patients with BR should undergo at least MP-MRI of the prostate and bone scan. Biopsy of any suspicious lesions within the prostate gland on MP-MRI is encouraged.

Freedom from Biochemical (PSA) Recurrence (FFBR):

The time to PSA failure will be measured from the date of treatment to the date of a rise by 2 ng/mL or more above the nadir PSA. The time of failure will be the date of the first PSA that is 2 ng/mL or more above the lowest prior post-treatment PSA value. If the rise in PSA to $>$ nadir + 2 occurs during the first 36 months followed by a subsequent non-hormonal induced PSA decrease, patients will **not** be considered PSA failures.

As a benign “spike” or “bounce” in the PSA value has been described in as many as 35% of patients 12-36 months following brachytherapy, intervention for a PSA failure should be based on a positive prostate biopsy at least 24 months post-treatment and/or clinical evidence of distant relapse (i.e., bone scan, CT scan, etc).

Local Failure (LF): This rating will be assigned when there is biopsy-proven disease progression or recurrence at the lesion within the prostate treated with protocol therapy. Histologic criterion for local failure is the presence of prostatic carcinoma upon biopsy more than 2 years after the start of treatment. Residual carcinoma on biopsy should show minimal radiation effect and should be in clinical scenario of increasing PSA.

Local Control (LC): Absence of local failure. This will be assumed in patients with a controlled PSA and for those with PSA failure but no radiographic, clinical, or biopsy-proven disease at the lesion treated with protocol therapy.

Freedom from Local Failure (FFLF): The time to local progression will be measured from the date of treatment to the date of local failure.

Elsewhere Prostate Failure (EPF): This rating will be assigned when there is biopsy-proven disease progression/recurrence at outside the lesion treated with protocol therapy but within the prostate or seminal vesicles.

Elsewhere Prostate Control (EPC): Absence of EPF. Will be assumed in patients with a controlled PSA and in patients with PSA failure but no radiographic, clinical, or biopsy-proven disease at the site treated with protocol therapy.

Freedom from Elsewhere Prostate Failure (FFEPF): The time to elsewhere prostate failure will be measured from the date of treatment to the date of EPF.

Regional Failure (RF): Visible disease on imaging that occurs in lymph nodes within the usual regional spread pattern of prostate cancer

Regional Control (RC): Absence of regional/nodal recurrence.

Freedom from Regional Failure (FFRF): The time to regional failure will be measured from the date of treatment to the date of RF.

Distant Metastasis (DM): Visible disease on imaging that occurs elsewhere in the body including non-regional lymph nodes.

Freedom from Distant Metastasis (FFDM): The time to distant metastasis will be measured as the date of treatment to the date of DM.

Freedom from hormone therapy (FFHT): The time from the date of treatment to first administration of androgen deprivation therapy

Disease-free Survival (DFS): Defined as the duration of time from the date of completion of treatment to either BR, LF, EPF, RF, DM, or death.

Cause-specific Survival (CSS): Defined as the duration of time from the date of completion of treatment to death from prostate cancer.

Overall Survival (OS): Defined as the duration of time from the date of completion of treatment until death from any cause.

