7.0 HORMONE THERAPY

Other than androgen deprivation therapy, patients must not receive other cancer-directed therapy (including standard fractionated radiotherapy, chemotherapy, biological therapy, and surgery) while on-study except at disease progression.

Standard institutional practices for neoadjuvant/concurrent and adjuvant short-term (6 months) androgen deprivation hormonal therapy will be used with the salvage

radiotherapy regimen. When possible, radiotherapy will begin approximately 2 months after the start of hormonal therapy. Some patients may have received prior hormonal therapy, but still require 6 months with the trial.

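### Requiring two follow-up PSAs for disease-control evaluability can drop early deaths and early imaging failures together with their events, which can bias DFS and OS upward

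*Combined protocol and SAP*

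**What the plan says.** Section 9.1.1 sets two populations. All men are evaluable for toxicity. For disease control the rule is narrower: "All patients with at least 2 follow-up PSAs will be evaluable for disease control". It continues: "After brachytherapy, these patients will have their disease status classified according to the definitions stated below". The definitions below it cover biochemical recurrence, local, elsewhere-prostate and regional failure, distant metastasis, freedom from hormone therapy, DFS, CSS and OS.

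The DFS definition reads "Defined as the duration of time from the date of completion of treatment to either BR, LF, EPF, RF, DM, or death", and the OS definition reads "Defined as the duration of time from the date of completion of treatment until death from any cause". Neither contains a PSA condition of its own.

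The Section 8.3 table has no PSA at Week 4. The scheduled follow-up PSAs are at Month 3, Month 6, Month 12 and then every 6 months.

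Sections 12.2 and 12.3 describe the efficacy analyses, including relapse-free status at 24 months. They name no analysis set, and they do not say how men with fewer than two PSAs are handled.

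**The concern.** Entry to the efficacy set depends on what happens after treatment. On the visit schedule, a man must be alive and in follow-up until about Month 6 to qualify, yet time at risk for DFS, CSS and OS starts at completion of treatment. Death, regional failure and distant metastasis can all be established without a PSA. A man who has one of these events and leaves before a second PSA is counted neither as an event nor as at risk.

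Each lost event raises the estimate for the endpoint it belongs to. Disease control is a stated secondary objective (Section 2.2.2), and Section 1.5 says the data are meant to support a later phase III trial. With only 24 men, one lost event is visible in the result.

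**Working it through.** **The plan's own figures.** The only design figures are for toxicity. Stage 1 continues with at most 1 toxic response in 7, and the null is rejected with at most 4 in 24. The probability of rejection is the sum over x = 0, 1 of P(Bin(7, p) = x) × P(Bin(17, p) ≤ 4 − x). This gives 0.0462 at p = 0.33 (stated .046) and 0.809 at p = 0.10 (stated 81%). The figures reproduce, and the PSA rule does not enter them. The plan gives no expected rate, power or sample size for any disease-control endpoint.

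**Which events the rule can remove** (definitions in Section 9.1.1, schedule in Section 8.3):

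- *Biochemical recurrence: not removed.* "The time of failure will be the date of the first PSA that is 2 ng/mL or more above the lowest prior post-treatment PSA value". A man needs an earlier post-treatment PSA to meet this, so he already has two.
- *Local failure: not removed early.* "Histologic criterion for local failure is the presence of prostatic carcinoma upon biopsy more than 2 years after the start of treatment". On the schedule, a man has several PSAs by then.
- *Regional failure and distant metastasis: can be removed.* They are defined by imaging alone. After baseline, bone scan and multi-parametric MRI are scheduled only at biochemical recurrence and PET/CT not at all, so an earlier failure would come from off-schedule imaging.
- *Death: can be removed.* It needs no PSA and no imaging.

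**Effect of losing early events.** Inputs: N = 24 (Section 12.2); E true DFS events by 24 months and k early-event men with fewer than two PSAs, both assumed. For simplicity every other man is followed to 24 months.

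- All men: (24 − E)/24
- Two-PSA set: (24 − E)/(24 − k)

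| E | all 24 men | k = 1 | k = 2 | k = 3 |
|---|---|---|---|---|
| 6 | 18/24 = 75.0% | 18/23 = 78.3% | 18/22 = 81.8% | 18/21 = 85.7% |
| 8 | 16/24 = 66.7% | 16/23 = 69.6% | 16/22 = 72.7% | 16/21 = 76.2% |
| 12 | 12/24 = 50.0% | 12/23 = 52.2% | 12/22 = 54.5% | 12/21 = 57.1% |

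Each additional lost event adds between 2.2 points (50.0% to 52.2%) and 3.9 points (81.8% to 85.7%). With k = 0 the two columns agree.

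**Effect of losing event-free dropouts.** Take 15 men event-free at 24 months, 8 with events between Months 8 and 22, and one who leaves event-free at Month 4. He is out of the risk set before the first event, so the Kaplan-Meier estimate is 15/23 = 65.2% with or without him. If he had instead died at Month 4, the estimate in all men would be 15/24 = 62.5%, against 65.2% in the two-PSA set.

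**The case against.** The strongest reply is that the rule was meant for PSA-based classification. It speaks of disease status, the OS and CSS definitions carry no PSA condition, and Section 12 does not repeat it. That reading is possible, so the reach to OS and CSS is the literal reading but not the only one. It does not remove the point. The text says "these patients will have their disease status classified according to the definitions stated below", the list below includes OS and CSS, Section 2.2.2 places both among the disease-control outcomes, and no other efficacy population is named.

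It is also fair to say that few men are likely to be affected. Candidates are ECOG 0 to 2, without distant metastases at entry, and on androgen deprivation, and early imaging failures would be found only off schedule. The number lost may be zero. The endpoints are secondary and descriptive.

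Four stronger readings are tempting and are not supported:

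- *Every efficacy endpoint is inflated, including by early progression.* Early biochemical failures already have two PSAs, and local failure by its histologic criterion cannot occur in the first 2 years.
- *Early dropout inflates the results.* Event-free dropouts leave Kaplan-Meier unchanged. Dropout related to prognosis could bias it, but ordinary censoring would not cure that either.
- *Each man gets about 6 months of guaranteed event-free time.* The rule requires two PSAs, not freedom from events. A man with imaging failure at Month 4 who has his Month 6 PSA is included with his event. An unscheduled PSA could also qualify a man earlier.
- *The qualifying PSAs are uninformative because of hormone therapy.* Section 7.0 says "radiotherapy will begin approximately 2 months after the start of hormonal therapy", with 6 months in total, so early values may reflect suppression. That is a separate question about PSA interpretation, and changing the analysis set does not address it.

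**Conclusion.** The concern holds in limited form. As written, the two-PSA rule can remove men who die early, or who have early regional or distant failure on imaging, together with their events. This can bias DFS and OS upward, and CSS, freedom from regional failure and freedom from distant metastasis when their own event is the early one.

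In the scenarios above (6 to 12 true events in 24 men), each lost event is worth roughly 2 to 4 percentage points. The number of such men is an assumption, since the documents give no early-event rate. A reader might infer that disease control will be overstated, or that OS is 100% to about Month 6 by construction. The first requires at least one lost early event. The second requires the literal reading of the rule and that only scheduled PSAs count.

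The toxicity endpoint, sample size, error rates and stage-1 rule are unaffected. This should be fixed, but it does not threaten the primary analysis.

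**What to change.** In Sections 9.1.1 and 12.3:

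1. Include all men who receive any protocol radiotherapy in the analyses of DFS, CSS, OS, freedom from regional failure and freedom from distant metastasis.
2. State one time origin. Section 9.1.1 currently uses the date of treatment for the freedom-from endpoints and the date of completion for DFS, CSS and OS. The origin chosen must also exist for a man who starts but does not complete treatment.
3. Count early deaths and failures as events wherever the endpoint's definition includes them, and censor the remaining men at their last relevant assessment (last contact for OS and CSS).
4. Keep the two-PSA set only as a labelled sensitivity analysis of freedom from biochemical recurrence.
5. Report how many men have fewer than two follow-up PSAs, and why.

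The cost is wording. No new data are needed, because Section 13.6.1 already has survival status and adverse events entered in the database. The estimates may come out slightly less favourable.
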